4.2.1.1.7 Ongoing

Ongoing is derived from the last daily intensity of the solicited period computed as described in [Section 4.2.1.1.1](#) and the maximum intensity in the ongoing period. The Investigator’s ongoing flag is not used because the measurement would determine the ongoing status of the reaction.

- Ongoing: if the last daily intensity of the solicited period is at least Grade 1 and the maximum intensity on the ongoing period is at least Grade 1
- Not ongoing: if the last daily intensity of the solicited period is None or the maximum intensity on the ongoing period is None
- Missing: all other conditions (in this case, it is not included in the denominator of the ongoing analysis in the safety tables)

Ongoing status will be derived for main analysis, sensitivity analysis and complementary analysis. Ongoing status is derived from the general method mentioned above for sensitivity analysis and complementary analysis. Ongoing status for main analysis is derived as follows:

- If ongoing status for sensitivity analysis is ongoing or missing, the ongoing status will be missing
- If ongoing status for sensitivity analysis is not ongoing, the ongoing status will be analyzed as not ongoing

4.2.1.2 Unsolicited AEs

Unsolicited AEs include unsolicited non-serious AEs, immediate unsolicited AEs, SAEs, AESIs and MAAEs. Analysis for unsolicited AEs only include those AEs collected within 21 days after each injection. SAEs, AESIs and MAAEs collected out of this range will only be presented in the analysis of SAEs/AESIs and MAAEs.

4.2.1.2.1 Presence

An observation was considered an event if it had at least a verbatim term and was not a Grade 0 intensity event.

Grade 0 events will not be included in safety analysis but will be included in separate listings.

4.2.1.2.2 Intensity

Intensity for unsolicited AE will be derived according to the following classification: None, Grade 1, Grade 2, Grade 3, or Missing.

If the unsolicited AE is measurable and its preferred term is part of the list of solicited reactions, then the measurement is derived based upon and following the same rule of the intensity scales defined in the protocol for that measurable injection site or systemic reaction.

Note the intensity could be considered “None” (not a reaction) in the analysis despite being considered a reaction by the investigator (eg, swelling measurement > 0 mm but < 25 mm in adults).

Intensity for the other unsolicited AEs will correspond to the value reported in the eCRF.

The maximum intensity corresponds to the highest intensity for a unique term.

Main analysis, sensitivity analysis and complementary analysis will be applied by maximum intensity. The maximum intensity for sensitivity analysis and complementary analysis is derived

by the general method mentioned above. Suppose a participant receiving an authorized/approved COVID-19 vaccine on Day X, the maximum intensity for main analysis is as follows:

- If an unsolicited AE for the participant with both time of onset and stop date before Day X, then the maximum intensity for that AE will be analyzed as collected in CRF.

If an unsolicited AE for the participant with time of onset before Day X and the corresponding stop date is on or after Day X, then the maximum intensity for that AE will be analyzed as Missing.

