3.4.3 Primary Endpoints - Safety

The main parameter will be described for all safety endpoints. The percentage of participants (using as denominator the number of participants) will be provided for analysis of solicited AEs, unsolicited AEs (including immediate systemic AEs within 30 minutes), SAEs, AESIs and MAAEs. The corresponding 95% CIs for the percentages will be calculated based on the Clopper--Pearson method. In the priming vaccine groups (comparator for Cohorts 1 and 2), subgroup analyses will be performed by age group (18-55 years and ≥ 56 years), high-risk medical conditions group, and baseline SARS-CoV-2 Naïve status for main safety analyses. In the booster vaccine groups (in Cohorts 1 and 2), subgroup analyses will be performed by age group (18-55 years and ≥ 56 years), high-risk medical conditions group, priming vaccine platform and individual priming vaccine. Safety endpoints will be analyzed for each of the CoV2 preS dTM primary series dosage administered in the original Phase II cohort (ie, 5-10-15 μ g) for Cohort 2.

Safety endpoints that occurred after authorized/approved COVID-19 vaccine injection will be listed separately.

SafAS population will be used for safety analyses for the following endpoints:

- Presence, and relationship of unsolicited (immediate) systemic AEs reported in the 30 minutes after each vaccination.
- Presence, time of onset, number of days of occurrence, intensity, action taken, and whether the reaction led to early termination from the study, of solicited (pre-listed in the participant's DC and CRF) injection site reactions and systemic reactions occurring up to 7 days after each vaccination.
- Presence, nature (Medical Dictionary for Regulatory Activities [MedDRA] system organ class [SOC] and preferred term [PT]), time of onset, duration, intensity, relationship to

vaccination and whether the event led to early termination from the study of unsolicited AEs reported up to 21 days after the last vaccination.

- Presence, nature (MedDRA SOC and PT), time of onset, seriousness criteria, relationship to vaccination, outcome, and whether the event led to early termination from the study, of SAEs.
- Presence, seriousness, intensity, nature (MedDRA SOC and PT), time of onset, duration, relationship to vaccination of all protocol-specified AESIs from the time of the first study vaccination throughout the study.

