4.2 Complementary Information on Derived Endpoints: Calculation Methods

4.2.1 Safety

Main analysis, sensitivity analysis and complementary analysis will be undertaken based on safety analysis set. Main safety analysis will be performed as the key safety results, sensitivity and complementary analysis will be performed as supportive results. The rationale for conducting the sensitivity and complementary analysis is because of the high likelihood for participants in the study to receive a non-study authorized/approved COVID-19 vaccine for Supplemental Cohorts Comparator group, and for Supplemental Cohort 1 and Cohort 2 booster arms, in case the participants receive a non-study authorized/approval COVID-19 vaccine after booster dose. These study participants will be allowed to continue study participation if they choose to do so; while continuation in the study will include all study procedures including safety follow-up and therefore safety data will be collected after receipt of a non-study authorized/approved COVID-19 vaccine which will interfere with interpretation of the safety data following study vaccination.

Main analysis will be applied for all safety endpoints. It includes all adverse events or reactions with time of onset before the date of receiving a non-study authorized/approved COVID-19 vaccine (if applicable) during study period. For some selected endpoints, main analysis will only include safety data collected before the date of receiving a non-study authorized/approved COVID-19 vaccine (censored by the date) corresponding to those adverse events or reactions included. For the other endpoints, safety analysis will include all data collected in the entire collection period corresponding to those adverse events or reactions. Details of conducting main analysis for those endpoints including censored data are further clarified in the following subsections.

Sensitivity analysis will be conducted for some selected endpoints. It includes all adverse events or reactions with time of onset before receiving a non-study authorized/approved COVID-19 vaccine during the study period and includes safety data collected over the entire collection period corresponding to those adverse events or reactions. Details of conducting sensitivity analysis for those specific endpoints are further clarified in the following subsections.

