Complementary analysis will be applied for some specific endpoints. It includes the adverse events or reactions with time of onset on or after receipt of a non-study authorized/approved COVID-19 vaccine (if applicable) during the study period and including all the corresponding safety data collected in the collection period. Details of conducting complementary analysis for those endpoints applicable will be clarified in the following subsections.

In general, sensitivity analysis will be conducted if there are at least 15 subjects with different values of the endpoint compared to the corresponding main analysis. Complementary analysis will be conducted if there are more than 15 subjects included in the corresponding analysis.

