4.2.1.2.8 Adverse Events of Special Interest

An event will be considered as an AESI if “Yes” is checked for “Is the event an AESI?” in the CRF. AESIs will be analyzed throughout the study using the following periods:

For Supplemental Cohort 1 and Cohort 2 booster arms:

- From D01 to 21 days post dose 1
- During the 6 months follow up period
- During the entire study (ie, all AESIs occurred during the study)

For Supplemental Cohorts Comparator group:

- D01 to dose 2 (including the day of dose 2, use 21 days after D01 if dose 2 is not received)
- Within 21 days post dose 2

- From D01 to 21 days post dose 2
- During the 6 months follow up period
- During the entire study (ie, all AESIs occurred during the study)

Note: AESI that occurred before vaccination (negative time of onset) will not be included in analysis but will be listed separately.

Main analysis and complementary analysis will be applied for AESIs.

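### In the main safety analysis, unsolicited AEs still present at a non-study COVID-19 vaccination are counted without a grade, and the table that restores the grade is in general produced only if at least 15 subjects differ

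*SAP*

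**What the plan says.** SAP section 4.2.1 defines three safety analyses around receipt of a non-study vaccine and ranks them: "Main safety analysis will be performed as the key safety results, sensitivity and complementary analysis will be performed as supportive results". The reason given is the "high likelihood for participants in the study to receive a non-study authorized/approved COVID-19 vaccine for Supplemental Cohorts Comparator group", and the same possibility in the booster arms. No rate is stated.

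For unsolicited AEs, section 4.2.1.2.2 keeps the CRF maximum intensity in the main analysis when the event both starts and stops before Day X. For any other event with earlier onset, the rule is that if "the corresponding stop date is on or after Day X, then the maximum intensity for that AE will be analyzed as Missing". The same section plans main, sensitivity and complementary analyses by maximum intensity.

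The rule has a wide scope, since section 4.2.1.2 states: "Unsolicited AEs include unsolicited non-serious AEs, immediate unsolicited AEs, SAEs, AESIs and MAAEs". Section 3.4.3 lists the parameters to be reported, among them "Presence, seriousness, intensity, nature (MedDRA SOC and PT), time of onset, duration, relationship to vaccination of all protocol-specified AESIs", and gives the corresponding list for MAAEs.

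Section 4.2.1 puts a condition on the supporting analysis: in general, "sensitivity analysis will be conducted if there are at least 15 subjects with different values of the endpoint" compared with the main analysis. Section 4.2.1.2.8 then says "Main analysis and complementary analysis will be applied for AESIs", and section 4.2.1.2.6 says the equivalent for MAAEs. Neither mentions a sensitivity analysis.

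**The concern.** Whether an AE spans Day X depends on how long it lasts, so the missing grades are not a random sample: a prolonged event is more likely to lose its grade than a short one. Compared with the grades in the CRF, the rule can only lower the graded counts, including Grade 3. The effect is greatest where non-study vaccination is most frequent, which the SAP expects in the Comparator Group. A side-by-side reading of severity in the Comparator and booster groups could therefore be distorted by outside vaccination rather than by the vaccines studied.

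The table that would show this is conditional, and its threshold is hardest to reach for uncommon outcomes such as Grade 3 events or AESIs. The AESI and MAAE sections also leave it unclear whether that table exists for them at all.

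**Working it through.** The SAP states no figure to reproduce, so the check follows one event through the planned analyses and then sizes the 15-subject condition.

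**Step 1. What each analysis does with an unsolicited AE in a participant vaccinated outside the study on Day X** (sections 4.2.1 and 4.2.1.2.2)

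| Event | Main | Sensitivity | Complementary |
|---|---|---|---|
| Starts and stops before Day X | Counted, CRF grade | Counted, CRF grade | Not included |
| Starts before Day X, stops on or after it | Counted, grade Missing | Counted, CRF grade | Not included |
| Starts on or after Day X | Not included | Not included | Counted, CRF grade |

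The last column follows from the definition of the complementary analysis: "It includes the adverse events or reactions with time of onset on or after receipt of a non-study authorized/approved COVID-19 vaccine". For the middle row, only the sensitivity analysis carries the grade. Section 3.4.7.1.3 leaves missing intensities of non-serious unsolicited AEs unimputed, so nothing later restores it. Section 4.2.1.2.5 also sets the duration of these events to Missing in the main analysis, so the table would not show that they were prolonged.

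**Step 2. AESIs and MAAEs.** Section 4.2.1.2 places both among unsolicited AEs, so the Missing rule of 4.2.1.2.2 reaches them, and so should the sensitivity analysis by maximum intensity planned in that section. Sections 4.2.1.2.6 and 4.2.1.2.8 list only main and complementary analyses. A programmer could follow either.

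**Step 3. How many subjects can be affected without triggering the table.** The threshold is 15, so up to 14. With group sizes from section 1 (Tables 1.2 and 1.3), if the count is made per group:

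- Comparator: 14/515 = 2.7%
- Cohort 1: 14/565 = 2.5%
- Cohort 2 D614 booster: 14/345 = 4.1%
- One exploratory arm: 14/100 = 14%

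**Step 4. Chance of reaching 15.** Let K be the number of subjects in a group whose value for the endpoint differs, with K ~ Binomial(N, p) and subjects independent. The SAP gives no p, so a range of 0.5% to 3% is assumed. P(K ≥ 15) is:

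| Group | N | p = 0.5% | p = 1% | p = 2% | p = 3% |
|---|---|---|---|---|---|
| Comparator | 515 | <0.0001 | 0.0003 | 0.10 | 0.58 |
| Cohort 1 | 565 | <0.0001 | 0.0007 | 0.17 | 0.72 |
| Cohort 2 B.1.351 | 970 | 0.0002 | 0.07 | 0.87 | >0.99 |
| Cohort 2 D614 | 345 | <0.0001 | <0.0001 | 0.005 | 0.10 |

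The answer depends on the counting rule. Pooled over all 3660 planned participants, p = 1% gives an expected 3660 × 0.01 = 36.6 subjects, well above 15. The threshold is then equivalent to a share of 15/3660 = 0.41%. The SAP does not say which count applies.

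**The case against.** The rule has a sound reason. The SAP works from one maximum intensity per unsolicited AE, and for an event that spans Day X it shows nothing about whether that maximum was reached before or after the other vaccine. Solicited reactions have daily grades, so section 4.2.1.1.2 can cut them off at Day X-1; unsolicited AEs cannot be cut that way. Putting the CRF maximum into the main analysis risks error in the other direction. This stands: the choice of a censored main analysis is defensible, and the point does not require changing it.

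Safety is also descriptive, with percentages and exact intervals, so no formal test turns on these tables. The general unsolicited AE tables cover only onset within 21 days of an injection, which limits how many events span Day X there. The 15-subject condition is introduced as a general rule, so the table could still be run below it. All of this limits the consequence but does not give the reader the grade.

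Four stronger readings are tempting, and the SAP does not support them:

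- *That these events vanish from the tables.* Inclusion depends on onset before Day X (section 4.2.1), and only Grade 0 events are dropped (section 4.2.1.2.1). The events are counted with intensity Missing; seriousness and outcome are summarised as collected.
- *That no number of affected AESIs or MAAEs could ever trigger a sensitivity table.* If the Missing rule of 4.2.1.2.2 reaches them, so does its sensitivity analysis. For period counts of events, main and sensitivity analyses take the same events, so listing only main and complementary there may simply reflect that.
- *That intensity is itself a primary safety endpoint.* Table 2.1 defines the AESI and MAAE endpoints as presence. Intensity is an analysis parameter in section 3.4.3, and is not listed there for SAEs.
- *That 2.7 percentage points is the expected loss.* It requires all 14 affected subjects to be in the Comparator, each with a Grade 3 event spanning Day X.

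**Conclusion.** The point holds as a gap in reporting. In the key safety tables, unsolicited AEs that outlast a non-study vaccination are counted without a grade. The loss falls selectively on longer events, and the only analysis that shows the grade is in general conditional on 15 differing subjects under an unspecified counting rule. For AESIs and MAAEs, sections 4.2.1.2.6 and 4.2.1.2.8 must be reconciled with section 4.2.1.2.2.

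The direction relative to the recorded grades is clear: graded counts can only fall. Whether the recorded grade is the right one to attribute to study vaccine is uncertain for each such event. The amount is unknown. For one application of the threshold within the Comparator Group, the ceiling is 14/515 = 2.7%. With per-group counting and an assumed affected share of 1 to 2%, the Comparator table would be triggered with probability between 0.0003 and 0.10. These probabilities rest on the assumed share, on independence between subjects and on per-group counting; pooled counting would make the condition much easier to meet.

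**What to change.** Keep the censored main derivation in section 4.2.1.2.2 if the sponsor wishes, and change three things:

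1. Exempt maximum intensity from the 15-subject condition in section 4.2.1. Always produce the sensitivity table for unsolicited AEs, AESIs and MAAEs, using the CRF grade for every event with onset before Day X and flagging those that stop on or after Day X.
2. Amend sections 4.2.1.2.6 and 4.2.1.2.8 so that they list the sensitivity analysis by maximum intensity, in line with section 4.2.1.2.2.
3. Where the 15-subject condition stays for other endpoints, state whether subjects are counted per group, per endpoint or overall.

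This needs SAP wording and one additional set of tables, with no new data. The tables may be sparse, and some flagged grades may have been reached after the other vaccine; the flag tells the reader which ones are open to that doubt.

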4.2.1.2.3 Last Vaccination

The last vaccination before an unsolicited AE is derived from the start date of the unsolicited AE provided in the clinical database and is calculated as follows:

- If an unsolicited AE has a complete start date and different to any of the vaccination dates, the start date is used to determine the last vaccination before the unsolicited AE.
- If the start date is missing or partially missing, or equal to any vaccination date, then the visit number in the “Appeared after Visit” or similar field, is used to determine the last vaccination before the unsolicited AE.

NOTE: This vaccination refers to the last study vaccination and not to a non-study authorized/approved COVID-19 vaccination.

4.2.1.2.4 Time of Onset

Time of onset is derived from the start date of the unsolicited AE provided in the clinical database and the date of last vaccination as described in [Section 4.2.1.2.3](#):

- Time of onset = start date of the unsolicited AE – date of last vaccination before the unsolicited AE + 1

The time of onset should be considered as missing only if one of or both the dates are missing or partially missing.

The unsolicited AEs will be analyzed “Within 21 days”, which corresponds to AEs with a time of onset between 1 and 22 days or missing.

An AE with missing time of onset will be considered to have occurred just after the vaccination indicated by the visit number in “Appeared after visit” or similar field, so will be included in these tables.

Time of onset will be categorized into and displayed as 1-4 days, 5-8 days, 9-15 days, 16 days or later, and Missing.

Note: To further clarify the analysis:

- Any unsolicited AEs collected throughout the study (SAEs, MAAEs, AESIs) with time of onset > 22 days after each injection will not be presented in tables of unsolicited AEs within 21 days but only in tables of SAEs, MAAEs, AESIs.

- Any unsolicited AEs (planned to report up to 21 days) with time of onset between 1 and 22 days or missing after each injection will be presented in the tables of unsolicited AEs within 21 days.
- Any unsolicited AEs (planned to report up to 21 days) with time of onset > 22 days after the 1st injection will not be presented in any tables but listed separately.
- Any unsolicited AEs with null (0) or negative time of onset will be excluded from the above tables and listed separately.

Main analysis and complementary analysis will be applied by time of onset.

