3.4.7.1.1 Immediate

Unsolicited systemic AEs with a missing response to the “Immediate” field will be assumed to have occurred within the 30-minute surveillance period.

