3.4.7.1.4 Start Date and End Date

Missing or partially missing start dates or end dates for unsolicited AEs (including SAEs) will remain missing and not be imputed. If the start date is missing or partially missing, the time of onset will be considered to be missing. Nevertheless, unsolicited AEs with missing time of onset will be included in analyses according to the last vaccination (computed according to the [Section 4.2.1.2.3](#)). If either the start date or end date is missing or partially missing, the duration will be considered missing.

Missing or partially missing end dates for ongoing solicited AEs will remain missing and not be imputed.

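### A partly missing start date can put a late SAE, AESI or MAAE in the 'Within 21 days' unsolicited AE tables, and a blank 'Immediate' field makes a systemic AE a 30-minute event, even when the recorded dates rule this out

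*SAP*

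**What the plan says.** Section 3.4.7.1.4 gives the starting rule for unsolicited AEs: "Missing or partially missing start dates or end dates for unsolicited AEs (including SAEs) will remain missing and not be imputed". It continues: "If the start date is missing or partially missing, the time of onset will be considered to be missing". These events are still analysed, under the last vaccination.

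Section 4.2.1.2.3 says how that vaccination is found. When the start date is incomplete, the visit number in the 'Appeared after Visit' field "is used to determine the last vaccination before the unsolicited AE". Only study vaccinations count, and no upper limit is set on the time since vaccination.

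Section 4.2.1.2.4 defines the 'Within 21 days' analysis by a condition "which corresponds to AEs with a time of onset between 1 and 22 days or missing". It adds: "An AE with missing time of onset will be considered to have occurred just after the vaccination indicated by the visit number in" the 'Appeared after visit' field, and says that the AE therefore goes into these tables.

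Section 4.2.1.2 counts SAEs, AESIs and MAAEs as unsolicited AEs, limits the unsolicited AE analysis to 21 days after each injection, and states: "SAEs, AESIs and MAAEs collected out of this range will only be presented in the analysis of SAEs/AESIs and MAAEs".

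Section 3.4.7.1.1 covers unsolicited systemic AEs whose 'Immediate' field is blank. They "will be assumed to have occurred within the 30-minute surveillance period". No condition on the start date is given.

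**The concern.** Placing an event in the risk window is a reasonable worst case when nothing is known about its date. It is not reasonable when the recorded month, or the visit after which the event appeared, shows that it began outside the window. SAEs, AESIs and MAAEs are collected for the whole study, so they can begin many months after the last injection and still have an incomplete start date. The 'Immediate' rule has the same weakness: the start date may be complete and later than the vaccination day, and the rule does not look at it.

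Both windows define primary safety endpoints in Table 2.1: unsolicited systemic AEs in the first 30 minutes, and unsolicited AEs up to 21 days after the last vaccination. What is at stake is their accuracy. Events that the database itself shows to be late could be reported as early. If causality is also missing for a systemic event, 3.4.7.1.2 counts it as related as well.

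**Working it through.** The SAP states no figure here, so there is none to reproduce. The check follows one event through the rules and then illustrates the size.

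**1. One event through the rules (assumed dates).** Booster on 15 September 2021; MAAE with start date recorded as May 2022, day missing.
- Onset formula in 4.2.1.2.4: start date − date of last vaccination + 1.
- Earliest possible onset: 1 May 2022 − 15 September 2021 + 1 = day 229.
- Latest possible onset: 31 May 2022 − 15 September 2021 + 1 = day 259.
- 3.4.7.1.4: the start date is partly missing, so onset is missing.
- 4.2.1.2.3: booster participants receive one study injection, so the event is assigned to it.
- 4.2.1.2.4, general sentences: missing onset is inside the 21-day definition, so the event is tabulated there.

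The event cannot have begun before day 229, yet it is counted in a window that ends on day 22.

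**2. Does other text stop this?**
- 4.2.1.2 sends out-of-range SAEs, AESIs and MAAEs to their own tables only. But 4.2.1.2.4 defines the range to include missing onset.
- The first bullet of the note in 4.2.1.2.4 keeps SAEs, MAAEs and AESIs out of the 21-day tables when onset exceeds 22 days. A missing onset does not meet that condition.
- The second bullet puts missing onset into the 21-day tables, but for AEs whose planned reporting period is 21 days. It does not cover events collected throughout the study.
- Neither bullet therefore places a late SAE, MAAE or AESI with a partial date. The general sentences do place it, in the 21-day tables.

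**3. The 'Immediate' field.** Take an unsolicited systemic AE with a complete start date giving onset on day 10 and a blank 'Immediate' field. Under 3.4.7.1.1 it is a 30-minute event.

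**4. How much the recorded month would resolve.** Assume onset spread evenly over 366 days, only the day missing, and vaccination dates spread over 365 calendar days.
- Truly in the window: 22/366 = 6.0%.
- Month still compatible with the window: about 10.0%.
- Excluded by the month alone: about 90.0%.
- Counted under the general wording: 100%.

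**5. Effect on a 515-participant arm.** Extra participants = 515 × (share with a late MAAE) × (share of those with a partial date). Both shares are assumptions.
- Low end: 515 × 0.10 × 0.01 = 0.5 participants, or 0.1 percentage points.
- High end: 515 × 0.30 × 0.05 = 7.7 participants, or 1.5 percentage points.

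For the assumed shares these are upper values, because a participant who already has an unsolicited AE in the window adds nothing to the percentage.

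**The case against.** The other side has several good points.

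- **The text can be read more narrowly.** The second bullet of the note ties missing onset to AEs planned for 21-day reporting, and 4.2.1.2 keeps out-of-range events in their own tables. Read together, these could exclude a month-8 MAAE. This stands as a possible reading. It does not remove the problem, because the general sentences are unrestricted and nothing says where such an event goes instead. A reader might infer that the plan plainly counts every AE with a partial date as early. The documents support only a conflict for SAEs, MAAEs and AESIs.
- **The convention is cautious and the data stay visible.** It over-counts harm, safety is descriptive with no hypothesis test, and the onset breakdown has a 'Missing' category. This stands and limits the consequences. The overall counts would still include the events.
- **The 'Immediate' limb depends on the CRF.** The SAP does not show whether the field is offered for late events, so how often it is blank for them is unknown. This stands on frequency. The rule as written still has no date check, though it covers unsolicited systemic AEs only.
- **Large relative figures mislead.** A reader might calculate that, with MAAEs spread evenly over 366 days and a fraction m partly dated, the booster-arm MAAE count in the window rises by 344/22 × m = 15.6m, or 16% at m = 1% and 78% at m = 5%. That describes the MAAE subset at an assumed m. It is not the effect on the primary endpoint, which is the percentage of participants with any unsolicited AE.

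**Conclusion.** The point holds as a cheap correction of low to moderate importance. On the general wording of 4.2.1.2.4, a late SAE, MAAE or AESI with only the day missing is tabulated within 21 days even when its month rules that out. This conflicts with 4.2.1.2 and is left open by the note. Section 3.4.7.1.1 can class an unsolicited systemic AE as a 30-minute event against its own recorded start date.

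The size is not derivable from the SAP, which gives no rate of partial dates or blank fields. The range of 0.1 to 1.5 percentage points in a 515-participant arm rests entirely on the assumed 10% to 30% with a late MAAE and 1% to 5% of those with a partial date.

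A reader might also infer that the separate MAAE, SAE and AESI period tables (4.2.1.2.6 to 4.2.1.2.8) are inflated, or that real early signals would be hidden. Those sections contain no rule for missing onset, so carry-over to them is an inference from 4.2.1.2.4 and is not stated. With descriptive analyses and a visible 'Missing' onset category, the documents do not show that signals would be hidden.

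**What to change.** **Section 4.2.1.2.4.** When the start date is incomplete, use the known date parts and the 'Appeared after Visit' field to find the earliest possible onset. If that falls after day 22 counted from the last study vaccination, leave the AE out of the 'Within 21 days' tables and show it only in the SAE, AESI and MAAE tables. Keep the rule that missing onset counts as in-window only where an in-window date remains possible. Say that this covers SAEs, AESIs and MAAEs, so that the general sentences and the note agree.

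**Sections 4.2.1.2.6 to 4.2.1.2.8.** Apply the same rule to the early periods, which now have no rule for missing onset.

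**Section 3.4.7.1.1.** Treat a blank 'Immediate' field as immediate only if the start date equals, or could equal, a study vaccination date.

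**Cost.** A few sentences in the SAP and a small programming change, with no new data. The SAP already uses partial dates elsewhere: 3.4.7.2 imputes a missing day for prior COVID-19 vaccination dates. The cautious default stays wherever the date is truly open.
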